14.3 Data Analysis

Demographic and clinical characteristics of the sample, as well as toxicity by grade and loss to follow up will be summarized using descriptive statistics. Overall response rate (ORR) and clinical benefit rate (CBR) will be evaluated using the RECIST 1.1 criteria according to investigator's assessment, and their 1-side 90% confidence intervals will also be calculated. Kaplan-Meier product limit estimator will be used to describe the distribution of overall survival (OS) and progression free survival (PFS). The association between response and the immunophenotype of peripheral blood immune cells will be summarized using descriptive statistics. Although data analysis will be primarily descriptive, permutation test will be used to rank the strength of association. Specifically, we first compute the observed test statistics for the differences between responders and non-responders. Then the null distribution of the test statistics will be generated by simulating 10,000 datasets where the status of response was randomly shuffled. The permutation p-values equal the proportion of simulations from the null distribution that exceed the observed test statistics. Similar analysis will be performed for the association between response and the changes in tumor immune cell infiltrate after treatment.

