1.6 Amendment #3 Study Continuation

1.6.1 Synopsis

The primary objective of the RamAtezo trial is to determine the overall response rate for the combination of ramucirumab and atezolizumab in patients with NSCLC previously treated with immune checkpoint blocker. This is an unmet need where there are few treatment options for patients after tumor progression on immune checkpoint blockers, particularly when used in combination with platinum-based doublet in the first-line setting.

The study design uses a Simon's two-stager MiniMax design where 12 patients are enrolled into the stage I. In case of one or more responses, the study will accrue 9 more patients, with a total of 4 responders indicating the preliminary evidence of efficacy.

Although there were no responses among the initial 12 patients, 8 patients had tumor reduction from baseline, including patient reaching 27% reduction, only 3% below the threshold for the RECIST criteria for response. Furthermore, the treatment has been well tolerated and 3 out of the 12 patients (25%) are still on treatment with progression-free survival higher than 6 months.

Therefore, we believe that the study should continue with the accrual of the additional 9 patients with the primary endpoint remaining the overall response rate. In this case, the Minimax design will be replaced by a simple enrollment of 21 patients.

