14.2 Study Design

This single institution study will be designed using Simon's two-stage MiniMax design. We plan to enroll twenty-one (21) advanced-stage NSCLC patients.

Assuming a null hypothesis of ORR less than 5% in this setting, we hypothesize that ORR of 20% or higher warrants further investigation. A total number of 21 patients allows an 80% power at 1-sided alpha of 0.1 to detect the expected difference. If 4 or more responders are observed at the end of the trial, we would conclude that there is preliminary evidence for efficacy warranting further investigation.

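### Section 14.3 plans only a one-sided 90% interval for ORR and CBR, with direction and method unstated; a two-sided exact interval would also address the 20% rate

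*Combined protocol and SAP*

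**What the plan says.** Section 14.3 gives the precision of the primary endpoint in one clause. ORR and CBR are assessed by the investigator under RECIST 1.1, and "their 1-side 90% confidence intervals will also be calculated". No direction, method or second limit is given.

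Section 14.2 sets the reference rates: "Assuming a null hypothesis of ORR less than 5% in this setting", and "we hypothesize that ORR of 20% or higher warrants further investigation". It adds that "A total number of 21 patients allows an 80% power at 1-sided alpha of 0.1 to detect the expected difference". The efficacy conclusion is tied to a count: "If 4 or more responders are observed at the end of the trial", preliminary efficacy is concluded. No null or target rate is given for CBR.

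Section 1.6.1 (Amendment 3) reports that "there were no responses among the initial 12 patients". It continues accrual by 9 patients to a single enrolment of 21, with ORR still the primary endpoint.

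**The concern.** The primary objective is to determine the ORR, which is an estimation aim, and one bound does not bracket an estimate. Two rates matter: 5%, which the test addresses, and 20%, the rate said to justify further work. A lower bound can speak to the first and an upper bound to the second. The plan commits to one bound without saying which.

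After 0/12, low final counts are the likely ones. The most useful statement may then be whether 20% is ruled out, and the planned interval may not supply it. With direction and method open, both could also be chosen after the count is known, in a single-arm trial with investigator-assessed response. For CBR there is no test for a one-sided bound to match.

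**Working it through.** **Inputs.** Null 5%, target 20%, N = 21, one-sided alpha 0.1 and power 80% (Section 14.2); 0 of 12 responders so far and 9 patients to come (Section 1.6.1); one-sided 90% level (Section 14.3). Assumption: all 21 patients are evaluable for response. Section 5.2 allows fewer.

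**1. The plan's own figures.** With X ~ Bin(21, p):
- Success at 3 or more: P(X ≥ 3 | 5%) = 0.085 and P(X ≥ 3 | 20%) = 0.821.
- Success at 4 or more, as stated: P(X ≥ 4 | 5%) = 0.019 and P(X ≥ 4 | 20%) = 0.630.
- An exact search for the Simon minimax design gives 12 then 21 patients, stopping at 0/12, with success at 3 or more: alpha 0.080, power 0.803.

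So N = 21 with 80% power at alpha 0.1 reproduces with a cut-off of 3, not with 4.

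**2. Likely final counts after 0/12.** The final count equals the responders among the next 9, Y ~ Bin(9, p).
- p = 5%: P(Y ≤ 2) = 0.630 + 0.299 + 0.063 = 0.992.
- p = 20%: P(Y ≤ 2) = 0.134 + 0.302 + 0.302 = 0.738.

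**3. One-sided 90% bounds at n = 21.**
- Exact (Clopper-Pearson): lower = Beta quantile at 0.10 with parameters (x, 22 − x), and 0 when x = 0; upper = Beta quantile at 0.90 with parameters (x + 1, 21 − x).
- Wald: x/21 ± 1.2816 × √[p̂(1 − p̂)/21], with p̂ = x/21.

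| Responders | Exact lower | Exact upper | Wald lower | Wald upper |
|---|---|---|---|---|
| 0 | 0 | 10.4% | 0 | 0 |
| 1 | 0.5% | 17.3% | −1.2% | 10.7% |
| 2 | 2.6% | 23.4% | 1.3% | 17.7% |
| 3 | 5.4% | 29.1% | 4.5% | 24.1% |
| 4 | 8.6% | 34.5% | 8.1% | 30.0% |

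Worked cases:
- 0/21, exact upper: 1 − 0.1^(1/21) = 0.104.
- 3/21, Wald lower: 0.1429 − 1.2816 × 0.0764 = 0.045.
- 2/21, Wald upper: 0.0952 + 1.2816 × 0.0641 = 0.177.

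**4. Effect of direction.** At 0 to 2 responders the exact lower bound runs from 0 to 2.6%: it fails to exclude 5% and does not address 20%. The exact upper limit excludes 20% at 0 and 1 responders but not at 2.

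**5. Effect of method.** Six methods were compared: exact, Wald, Wilson, Agresti-Coull, Jeffreys and mid-P.
- At 3/21 only the Wald lower bound (4.5%) falls below 5%; the others run from 5.4% to 7.1%.
- At 2/21 only the Wald upper bound (17.7%) falls below 20%; the others run from 20.4% to 23.4%.
- At 0/21 the Wald interval collapses to a point.

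**6. Effect of level.** For 1/21 the exact upper limit is 17.3% in a two-sided 80% interval and 23.8% in a two-sided 95% interval. For 3/21 the exact lower limits are 5.4% and 3.0%.

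**The case against.** A reader might infer that the report cannot say whether a 20% ORR is excluded. The text does not support that. It never says the bound is a lower one, and an upper bound would exclude 20% at 0/21 and 1/21 by every method checked. The lower-bound reading is natural beside a one-sided test, but it is an inference.

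A reader might also infer that the interval method decides the trial's conclusion at 3/21. It does not. Section 14.2 asks for 4 or more responders, so 3/21 fails whatever the interval, and at 4/21 every method excludes 5%. Given 0/12, exactly 3 responders is also unlikely: probability 0.008 at an ORR of 5% and 0.18 at 20%. Nothing says that Wald will be used.

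Finally, anyone holding the count and denominator can compute whichever bound is missing, so no information is lost, and this is a pilot study.

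These points limit the concern without removing it. Under either direction one of the two reference rates lacks its matching limit, and neither direction nor method is fixed before the final count is known.

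**Conclusion.** The concern holds as a gap in the planned estimation, not as a flaw in the efficacy decision. If the bound is a lower one, it does not address 20% at counts with a combined probability of 0.99 (ORR 5%) or 0.74 (ORR 20%) after 0/12. If it is an upper one, it does not match the test of 5%. Method matters at 2/21 and 3/21, where Wald falls on the other side of a reference rate from the other five methods, and at 0/21, where Wald gives no width.

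One conflict remains that no choice of interval settles. At 3/21 the exact lower bound (5.4%) and the exact one-sided p-value (0.085) reject 5% at the stated alpha, while the count rule declares no efficacy. This comes from the cut-off in Section 14.2, not from Section 14.3. Stating that the count rule governs would leave the mismatch with the stated 80% power and alpha 0.1 in place.

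The figures assume 21 evaluable patients and independent responses with a common rate.

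**What to change.** In Section 14.3, replace the one-sided interval with two-sided exact (Clopper-Pearson) 80% intervals for ORR and CBR, and state the denominator. The lower limit is then the exact one-sided 90% bound matching alpha 0.1. For ORR, name the upper limit as the one used to judge 20%.

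Add 95% exact intervals as description only, and note that exclusion of 20% depends on the level, as it does at 1/21.

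Separately, reconcile the cut-off of 4 in Section 14.2 with the stated power and alpha; do not rely on a precedence statement in Section 14.3 to do this.

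The change to Section 14.3 costs a sentence or two and needs no further patients or data.

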11.0 DATA SUBMISSION SCHEDULE

Case report forms with appropriate source documentation will be completed according to the schedule listed in this section.

Case Report Form	Submission Schedule
Original Consent Form	Prior to registration
On-Study Form	Prior to starting treatment
Treatment Form	Every cycle
Toxicity Form Concomitant Medications Form	Continuous. See Section 7.0 for reporting requirements
Research Tissue Form	Baseline, after Cycle 2/before Cycle 3
Research Blood Form	Baseline, C2D1
Treatment Summary Form	Completion of treatment
Follow Up Form	Every 3 months for 2 years
Death Form	Time of death
RECIST Form	Baseline, end of every even numbered cycle, and end of treatment
MedWatch Form	See Section 7.0 for reporting requirements

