Target lesions: All measurable lesions up to a maximum of 2 lesions per organ and 5 lesions in total, representative of all involved organs, should be identified as target lesions and recorded and measured at baseline. Target lesions should be selected on the basis of their size (lesions with the longest diameter), be representative of all involved organs, but in addition should be those that lend themselves to reproducible repeated measurements. It may be the case that, on occasion, the largest lesion does not lend itself to reproducible measurement in which circumstance the next largest lesion which can be measured reproducibly should be selected. A sum of the diameters (longest for non-nodal lesions, short axis for nodal lesions) for all target lesions will be calculated and reported as the baseline sum diameters. If lymph nodes are to be included in the sum, then only the short axis is added into the sum. The baseline sum diameters will be used as reference to further characterize any objective tumor regression in the measurable dimension of the disease.

Non-target lesions: All other lesions (or sites of disease) including any measurable lesions over and above the 5 target lesions should be identified as non-target lesions and should also be recorded at baseline. Measurements of these lesions are not required, but the presence, absence, or in rare cases unequivocal progression of each should be noted throughout follow-up.

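### Section 14.3 ranks immune markers only by responder versus non-responder, which cannot be computed with no responders and rests on one patient with one; a percent-change ranking should be added beside it

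*Combined protocol and SAP*

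**What the plan says.** Section 14.3 calls the analysis descriptive in the main ("Although data analysis will be primarily descriptive") but adds that a "permutation test will be used to rank the strength of association". The statistic is set out as follows: "we first compute the observed test statistics for the differences between responders and non-responders". Its null distribution comes from "simulating 10,000 datasets where the status of response was randomly shuffled". Changes in tumour immune infiltrate are to be handled in a similar way. No alpha, effect size or power is given for this ranking. Whether the test is one- or two-sided is also left open: "The permutation p-values equal the proportion of simulations from the null distribution that exceed the observed test statistics".

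The measurements behind response are collected. Section 12.2 states: "The baseline sum diameters will be used as reference to further characterize any objective tumor regression in the measurable dimension of the disease". Under Section 11.0 the RECIST form is due at "Baseline, end of every even numbered cycle, and end of treatment". Percent change is not named there as a field, but it follows directly from these sums.

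The amendment rationale in Section 1.6.1 already uses it. After reporting no responses among 12 patients, it says that "8 patients had tumor reduction from baseline, including patient reaching 27% reduction, only 3% below the threshold for the RECIST criteria for response".

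**The concern.** The contrast needs responders, and after the first 12 patients there were none. If the last 9 produce none, neither exploratory objective has a planned analysis that can be carried out. If they produce one or two, the order of the markers is set largely by those patients' values.

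The contrast also ignores differences in shrinkage among non-responders. The patient with the 27% reduction is placed in the same group as any patient who progressed, although Section 1.6.1 treats that reduction as a reason to continue the trial. RECIST categories are needed for ORR and CBR. A marker association does not need them, and Section 14.3 gives no reason for using them alone. What is at stake is whether the blood and tissue samples can address the exploratory objectives at all.

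**Working it through.** **Inputs from the documents.** Planned enrolment is 21 (Section 14.2). There were 0 responses in the first 12 (Section 1.6.1), which leaves 9 patients. The null and target ORR are 5% and 20% (Section 14.2). The 80% power in Section 14.2 belongs to the ORR test. No power is stated for the marker ranking, so there is no plan figure to reproduce here.

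**Assumptions.** The first 12 are taken as final non-responders. Three were still on treatment, so a late response is possible and would add to the count. Correlation, alpha and sidedness are not in the documents and are varied below.

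**Step 1: how many responders to expect.** With X ~ Binomial(9, p):

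- p = 0.20: P(0) = 0.8^9 = 0.134; P(1) = 9 × 0.2 × 0.8^8 = 0.302; P(0 or 1) = 0.436. P(4 or more) = 0.086.
- p = 0.05: P(0) = 0.95^9 = 0.630; P(1) = 9 × 0.05 × 0.95^8 = 0.299; P(0 or 1) = 0.929. P(4 or more) = 0.0006.

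**Step 2: what the statistic does at those counts.** With 0 responders one group is empty and the difference does not exist. With 1 responder among 21 there are only 21 distinct labellings, however many shuffles are drawn, so p-values move in steps of 1/21 = 4.8%. With 4 responders there are C(21,4) = 5,985.

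**Step 3: loss under a graded relation.** Marker and shrinkage were simulated as bivariate normal, and the k patients with most shrinkage were called responders. A permutation test of the mean difference was compared with a permutation Spearman test (n = 21, two-sided 0.10, 1,500 datasets; standard error of each power at most √(0.25/1500) = 1.3 points). At correlation 0.5:

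| Responders | Yes/no | Spearman | Difference |
|---|---|---|---|
| 1 | 19% | 70% | 51 |
| 2 | 30% | 70% | 39 |
| 3 | 40% | 73% | 33 |
| 4 | 45% | 71% | 26 |

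A separate run put the one-responder loss at about 49 points. With 4 responders, the loss at other correlations is about 5–12 points at 0.2–0.3 and about 20–27 at 0.4–0.6.

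The choice of test matters. At two-sided 0.05, rank-sum against Spearman loses 4, 10, 19, 28 and 34 points at correlations 0.2, 0.3, 0.4, 0.5 and 0.6. At one-sided 0.10 the same pair loses 8, 14, 20, 22 and 20.

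Repeat biopsies are taken only when feasible (Section 9.2), so the tissue analysis will probably have fewer patients. With 12 pairs, correlation 0.5 and two-sided 0.10, the loss is 33, 20, 14 and 12 points with 1, 2, 3 and 4 responders.

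**Step 4: ranking itself, with no alpha.** Assume 40 independent markers (Section 1.5 mentions about 40), one of them related to shrinkage at correlation 0.5, and n = 21. The related marker reaches the top five in 28%, 36%, 45% and 48% of datasets by the yes/no statistic with 1, 2, 3 and 4 responders, and in 73–74% by Spearman. With 4 responders the loss is about 13, 19, 25 and 25 points at correlations 0.3, 0.4, 0.5 and 0.6.

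**Step 5: what shrinks or reverses the gain** (n = 21, 4 responders, two-sided 0.10).

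- *Tied worst ranks.* Percent change misses new-lesion and non-target progression, so some patients need an assigned rank. At correlation 0.5, with 4 of 21 worst-ranked independently of marker and target-lesion change, power is 47% (yes/no) against 52% (Spearman). With 7 of 21 it is 46% against 40%. Across assumptions about how many are worst-ranked and why, the gain runs from about +23 to about −5 points.
- *Marker shifted only in responders.* For shifts of 1, 1.5 and 2 SD, yes/no has 51%, 84% and 97%, against 25%, 42% and 56% for Spearman.

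**The case against.** The strongest reply is that Section 14.3 matches its own objective. Sections 2.3 and 14.1 ask about the relationship with response, and Section 12.4 defines response by RECIST 1.1, including non-target and new lesions. Percent change in target lesions is a different quantity. The analysis is also exploratory, in a pilot of 21, with no significance threshold, so power is an imperfect yardstick.

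Most of this stands. It rules out two stronger readings that a reader might infer:

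- *That the yes/no ranking costs a fixed amount, about 25 points with 4 responders.* The documents do not fix any such figure. It needs a correlation near 0.5, an alpha and a graded relation, none of which they give. The loss is far smaller at weak correlations and changes sign if a marker acts only in responders. Four responders is itself a favourable case.
- *That percent change should replace the responder contrast.* That would leave the stated objective without its ranking, and the contrast is the better one under the responder-only model.

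The reply does not deal with few or no responders. Matching the objective does not help when the statistic cannot be computed. The argument about power is also weaker than it looks, because the loss appears in ranking itself (Step 4). A percent-change plot could always be made later, but by then it would be chosen after the marker results were known.

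**Conclusion.** The concern holds as a gap to fill, without showing that the planned contrast is wrong. The firmest part needs only the binomial distribution and the 0 of 12: the chance of no responder, and so no computable ranking, is 13% at a true ORR of 20% and 63% at 5%. The chance of 0 or 1 is 44% and 93%. These figures assume no late response among the first 12.

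The efficiency loss is conditional. Under a graded, bivariate normal relation with complete percent-change data, it is modest at weak correlations, about 20–27 points at moderate ones with 4 responders, and about 50 points with 1 responder at correlation 0.5. Tied worst ranks can remove it, and a responder-only marker effect reverses it. The documents do not say which model holds, which is the reason to report both rankings. ORR, CBR and the decision rule are not affected.

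**What to change.** In Section 14.3:

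- Keep the responder versus non-responder permutation ranking.
- Add a second ranking by the absolute Spearman correlation between each marker (or marker change) and best percent change from baseline in the sum of target-lesion diameters, using the same 10,000 permutations.
- Give the worst rank to patients whose first assessment shows new-lesion or non-target progression, and to those who die or progress clinically before any scan. Report how many patients are ranked this way.
- State that the percent-change ranking is the one reported if there are no responders, and that it is read as association with shrinkage and not with RECIST response.

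The cost is a few sentences and one more exploratory ranking to report, with no new data, visits or patients. Section 1.5 has the blood analyses batched at the end of study procedures, so if that batch has not been run the rule can still be set before any marker result is seen.

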of CD8+ T-cells in the periphery of patients ³⁶⁻³⁸, but despite this, the majority of patients will not derive meaningful benefit from this class of agents, and responses are often not durable. Blunting tumor angiogenesis in order to remodel the tumor microenvironment is an attractive combinatorial approach to synergize with standard immunoncology agents ³⁹. Increased VEGF expression is known to suppress the maturation of antigen-presenting dendritic cells and inhibit lymphocyte tracking into tumor tissues, which can limit the effectiveness of an antitumor adaptive immune response ⁴⁰. We hypothesize that the addition of ramucirumab will augment the clinical activity of atezolizumab, and in order to evaluate the exact mechanism of action of the combination, we propose a comprehensive analysis of paired peripheral blood samples collected longitudinally during this study. We will evaluate whether the combination of atezolizumab and ramucirumab (a) alters populations of circulating monocytes and myeloid derived suppressor cells, (b) increases the number and affects the phenotype of circulating NK cells, effector CD8+ and effector CD4+ T-cell subsets, (c) results in the generation of durable populations of memory CD8+ and CD4+ T-cells and (d) alters the ratio of circulating regulatory T-cells to effector CD8+ cells. We will utilize mass cytometry (CyTOF) for these analyses, a high dimensional technique that allows the assessment of ~40 individual markers using metal labeled antibodies to enable deep profiling of selected phenotypic and functional markers on individual cells as well as unique statistical analyses to simplify the interpretation of complex relationships of large numbers of cells ⁴¹⁻⁴³. We will collect and cryopreserve peripheral blood mononuclear cells prior to combination atezolizumab/ramucirumab therapy and again at the time of first radiographic assessment. Analyses will be completed in a batched fashion using an established mass cytometry panel at the The Andrew M. and Jane M. Bursky Center for Human Immunology & Immunotherapy Programs (CHiPs) at Washington University School of Medicine at the conclusion of study procedures to correlate immune profiles with clinical response. Patients will also undergo repeated biopsy to evaluate the differences in immune cell infiltrates between baseline and after two cycles of treatment.

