9.2 Biopsy Samples

When available, archival biopsy tissue will be used for a baseline biopsy. If baseline tissue is not available, the patient will undergo a baseline biopsy prior to initiation of the trial.

When feasible, a repeated tumor biopsy will be obtained between Cycles 2 and 3 after the scheduled CT scan.

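### The permutation p-value in section 14.3 counts only strictly larger statistics, so it can equal 0 and is too small, most of all for tied markers

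*Combined protocol and SAP*

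**What the plan says.** Section 14.3 calls the correlative analysis mainly descriptive, but adds that a "permutation test will be used to rank the strength of association". The procedure has three steps. First, "we first compute the observed test statistics for the differences between responders and non-responders". Next, a null distribution is built by "simulating 10,000 datasets where the status of response was randomly shuffled". Finally, "The permutation p-values equal the proportion of simulations from the null distribution that exceed the observed test statistics".

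The section does not name the test statistic, say whether the test is one- or two-sided, give a rule for ties, or count the observed labeling. No other section does so either. The procedure is then carried to tissue: "Similar analysis will be performed for the association between response and the changes in tumor immune cell infiltrate after treatment". Section 9.2 limits the data for that second use: "When feasible, a repeated tumor biopsy will be obtained between Cycles 2 and 3 after the scheduled CT scan".

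**The concern.** Under the null hypothesis the observed labeling is one draw from the set of possible labelings. The p-value is therefore the share of labelings at least as extreme as the observed one, and that share always includes the observed labeling. It cannot be 0. A rule that keeps only strictly larger statistics drops the observed labeling, every shuffle that redraws it, and every other labeling with the same value.

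Two things are at stake. A reported p of exactly 0 overstates the evidence, and section 1.5 describes a platform that "allows the assessment of ~40 individual markers using metal labeled antibodies", so such a value could appear in a long list and be read as conclusive. Also, the stated purpose is ranking. If the error differs between markers, the order can change.

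The error grows as labelings become fewer, and few are likely here. Section 1.6.1 reports: "Although there were no responses among the initial 12 patients".

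**Working it through.** **Inputs.** From section 14.2: 21 patients, with response rates of 5% (null) and 20% (target). From section 14.3: 10,000 shuffles. From section 1.6.1: 0 responses in the first 12 patients. Assumed, because the documents do not give them: k = 1 to 4 responders, complete samples in all 21 patients, the number of paired biopsies, and how markers are scored. The plan states no figure for this test, so there is none to reproduce.

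**1. Untied marker (every labeling gives a different statistic).** There are C(21,k) labelings. If the observed one is j-th from the most extreme, the plan's rule gives (j − 1)/C(21,k) and the valid value is j/C(21,k). The shortfall is 1/C(21,k) for every j, and the plan's p is 0 at j = 1.

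| Responders k | C(21,k) | Shortfall |
|---|---|---|
| 1 | 21 | 0.0476 |
| 2 | 210 | 0.0048 |
| 3 | 1,330 | 0.0008 |
| 4 | 5,985 | 0.0002 |

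The shift is the same for all untied markers measured in the same patients, so their order is unchanged.

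**2. Tied marker (illustration).** Take a present/absent marker, positive in P of 21 patients and in all k responders, with the absolute difference in proportions as the statistic. The observed value is 1 − (P − k)/(21 − k) = (21 − P)/(21 − k). The opposite extreme, no responder positive, gives P/(21 − k). For P ≤ 10 the observed value is the larger, nothing exceeds it, and the plan's p is 0. The valid p is C(P,k)/C(21,k).

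| k | P = 10 | P = 6 |
|---|---|---|
| 1 | 10/21 = 0.476 | 6/21 = 0.286 |
| 2 | 45/210 = 0.214 | 15/210 = 0.071 |
| 3 | 120/1,330 = 0.090 | 20/1,330 = 0.015 |
| 4 | 210/5,985 = 0.035 | 15/5,985 = 0.0025 |

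**3. Effect on ranking.** With 2 responders, the 10-of-21 marker has plan p = 0 and valid p = 0.214. An untied marker at its second most extreme labeling has plan p = 1/210 = 0.0048 and valid p = 2/210 = 0.0095. The plan puts the weaker marker first. With 4 responders, the 10-of-21 marker (valid 0.035) and an untied marker at its most extreme labeling (valid 0.00017) both get 0 and cannot be told apart.

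**4. Which part of the rule does the damage.** Among 10,000 shuffles the observed labeling is redrawn about 10,000/C(21,k) times: 476, 48, 7.5 and 1.7 for k = 1 to 4. All of these are discarded because they tie. Omitting the added 1 costs only about 1/10,001 = 0.0001. Nearly all the error therefore comes from the strict inequality. The added 1 is still needed: with 4 responders, 10,000 shuffles miss the observed labeling altogether with probability (1 − 1/5,985)^10,000 = 0.19.

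**5. How few responders to expect.** If none of the first 12 patients later responds, the total is binomial with 9 trials.

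| Response rate | P(0) | P(1) | P(2) | P(3) | P(0 or 1) |
|---|---|---|---|---|---|
| 5% | 0.630 | 0.299 | 0.063 | 0.008 | 0.929 |
| 20% | 0.134 | 0.302 | 0.302 | 0.176 | 0.436 |

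Exactly 1 responder, where the untied shortfall is largest, has probability about 0.30 at either rate. With 0 responders the test cannot be run.

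**6. Paired biopsies.** With m pairs the untied shortfall is 1/C(m,k). For m = 6, 8 and 12 this is 1/6 = 0.167, 1/8 = 0.125 and 1/12 = 0.083 with 1 responder, and 1/15 = 0.067, 1/28 = 0.036 and 1/66 = 0.015 with 2.

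**7. Size at 0.05 (illustrative only, since the plan sets no alpha).** With 1 responder of 21 and an untied marker, the plan's rule rejects for j = 1 or 2, which is 2/21 = 9.5%. The valid rule rejects for j = 1, which is 1/21 = 4.8%. With 10,000 random shuffles the figures are 8.9% and 4.1%.

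**The case against.** The best reply is about weight. The analysis is exploratory, no threshold or decision hangs on it, and untied markers keep their order. The mass cytometry measures in section 1.5 are mostly cell numbers, phenotypes and ratios, which rarely tie, and no section describes present/absent scoring. With complete data the untied shortfall is material essentially only at 1 responder. There the smallest valid p is 0.048 whatever the rule, so the scarcity of responders limits the analysis more than the inequality does. Finally, the verb may be loose prose for equal or exceed.

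Most of this stands, and it is why the point is minor. The present/absent figures are illustrations, and the size figures show direction only. Three things remain. Zero counts and infiltrate scores can tie, and the plan does not say how either is handled. Ties can also come from the unnamed statistic: with a two-sided rank statistic and 1 responder, ranks 1 and 21 lie equally far (10) from the mean rank of 11, so the valid p is 2/21 = 0.095 where the plan gives 0. And a programmer who follows the sentence would code a strict inequality; if something else was meant, the text should say so.

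**Conclusion.** The stated rule is wrong as written, not merely incomplete. It returns 0 at the most extreme labeling and understates the valid p-value elsewhere. For untied markers in 21 patients the understatement runs from 0.048 with 1 responder to 0.0002 with 4, is larger if fewer patients have samples, and leaves the ranking intact. For tied markers it can be several tenths and can reverse the ranking. That part depends on assumed marker patterns. The untied figures assume complete samples, and the responder probabilities assume no late response among the first 12 patients. The importance is minor: the primary endpoint and its conclusion are unaffected.

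**What to change.** Replace the p-value sentence in section 14.3 with wording such as:

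> The p-value is (1 + the number of shuffles whose statistic is at least as extreme as the observed one)/(10,000 + 1). Where there are 10,000 or fewer distinct labelings, all are enumerated, and the p-value is the proportion at least as extreme, the observed labeling included.

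Name the test statistic and its sidedness. A two-sided form based on the absolute value would be reasonable, but that choice is separate and belongs to the sponsor. Report the number of patients and responders in each comparison, and state that with no responders only the descriptive summaries are given. Apply the same text to the infiltrate analysis.

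The cost is a few sentences and a line of code, with no new data. Enumeration for up to 4 responders of 21 needs at most 5,985 labelings, fewer than the planned shuffles, and is optional because the corrected count alone removes the error. The only downside is slightly larger exploratory p-values for untied markers and appropriately larger ones for tied markers.
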